8.2 Rationale for study design

A crossover design was chosen to yield a more efficient comparison of treatments than a parallel study design, i.e., fewer subjects are required since each subject will serve as its own control. To avoid carryover effects, a wash-out period of at least 24 hours has been incorporated between administrations.

Randomization will be used to minimize bias in the assignment of subjects to a treatment sequence and to increase the likelihood that known and unknown subject attributes (e.g., demographic and baseline characteristics) are evenly balanced across treatment groups.

9 STUDY POPULATION

Prospective approval of protocol deviations to eligibility criteria, also known as protocol waivers or exemptions, is not permitted.

9.1 Recruitment

The subjects will be recruited from CTC's database of healthy volunteers and from advertising in media (including social media).

9.2 Screening and enrolment log

Investigator must keep a record of all screened subjects even if they were not subsequently included in the study. This information is necessary to verify that subjects were selected without bias. The reason for screen failure should be stated for all subjects screened but not included. The reason for withdrawal should be stated for all subjects included but not completed.

A screening number will be allocated to each subject in connection to the informed consent process at the Screening visit. The screening number is generated automatically in the electronic case report form (eCRF). The screening number will allow identification of subjects irrespective of their possible eligibility for the study.

Subjects included and randomized will be assigned a randomization number (101, 102 etc.).

If a subject cannot receive the planned dose of IP within 28 days after screening (*i.e.*, the time interval between signing informed consent until dose administration) the subject should be rescreened before proceeding in the study.

9.3 Number of subjects

36 subjects will be included in the study. Approximately 42 subjects will be screened to achieve 36 randomized subjects and 32 fully evaluable subjects.

For replacements of subjects who discontinue from the study, see Section 9.8.

9.4 Inclusion criteria

For inclusion in the study, subjects must fulfill the following criteria:

1. Willing and able to give written informed consent for participation in the study.

CONFIDENTIAL

- 2. Snus user who has used tobacco-based snus for ≥ 1 year, with a minimum weekly consumption of two or more snus cans, and is willing and able to use brands with nicotine content $\geq 1\%$.
- 3. Healthy male or female subject aged ≥ 19 years.
- 4. Women of child bearing potential (WOCBP) must be willing to use a sufficient contaceptive method for the duration of the study, this includes mechanical barrier (e.g., a male condom or a female diaphragm), combined [oestrogen and progestogen containing] hormonal contraception associated with inhibition of ovulation [oral, intravaginal, transdermal], progestogen-only hormonal anticonception associated with inhibition of ovulation [oral, injectable, implantable], IUD or IUS. Sexual abstinence is allowed when this is the preferred and usual lifestyle of the subject.

9.5 Exclusion criteria

Subjects must be excluded from the study if any of the following exclusion criteria are fulfilled:

- 1. Daily smoker, defined as smoking during the last 24 hours according to self-report.
- 2. A history or presence of diagnosed hypertension or any cardiovascular disease.
- 3. Any surgical or medical condition, or history thereof, which, in the judgment of the investigator, might interfere with the absorption, distribution, metabolism or excretion of the investigational product or may either put the subject at risk because of participation in the study, influence the results, or the subject's ability to participate in the study.
- 4. Female subject currently breast feeding, pregnant or planning to get pregnant during the study.
- 5. Any positive result on screening for serum hepatitis B surface antigen, hepatitis C antibody and Human Immunodeficiency Virus (HIV).
- 6. Positive screen for drugs of abuse or alcohol at screening or on admission to the unit prior to first administration of the IP.
- 7. Current or history of alcohol abuse and/or use of anabolic steroids or drugs of abuse, as judged by the investigator.
- 8. Plasma donation within one month of screening or blood donation (or corresponding blood loss) during the three months prior to screening.
- 9. Investigator considers the subject unlikely to comply with study procedures, restrictions and requirements.

9.6 Restrictions during the study

The subjects must be willing to comply to the following restrictions during the entire study duration i.e., from screening to the end-of-study visit.

9.6.1 *General restrictions*

• Subjects shall abstain from snus and all other nicotine containing products from 8.00 pm the night before the visit and during the visits (except the IP treatment).

- Subjects shall abstain from smoking the last 24 hours before each visit (from 8.00 am day before visit).
- Subjects are not allowed to eat or drink or conduct any other mouth related procedure (e.g. tooth brushing) 30 minutes before dose administration, during application of IP and 30 minutes after the IP have been taken out.
- Subjects shall abstain from drugs of abuse from Screening to the Follow-up visit.
- Subjects shall abstain from alcohol the last 12 hours before each visit (from 8.00 pm the night before visit).
- Subject must not donate blood or plasma during the study until three months after the Follow-up Visit.
- Subjects are not allowed to participate in any other clinical study during the study period i.e. screening to follow up.

9.6.2 **Prior and concomitant therapy**

No restrictions concerning concomitant medications or therapies.

9.7 Screen failures

Screen failures are defined as subjects who consent to participate in the clinical study but are not subsequently randomized in the study. A minimal set of screen failure information is required to ensure transparent reporting of screen failure subjects. Minimal information includes documentation of signed and dated informed consent form (ICF) and reason(s) for screening failure.

Subjects who do not meet the criteria for participation in this study may be rescreened.

Re-screening can be performed if any of the following were reasons for screening failure or non-randomization (as judged by the Investigator):

- Practical reasons.
- No significant medical conditions (e.g. influenza, nasopharyngitis).
- Reserve subject in previous cohort.
- Plasma or blood donation outside allowed time windows.

For subjects who are re-screened, a new screening number will be assigned and a new, signed ICF will be collected.

9.8 Subject withdrawal

9.8.1 General withdrawal criteria

Subjects are free to discontinue their participation in the study at any time and for whatever reason without affecting their right to an appropriate follow-up investigation or their future care. If possible, the reason for withdrawal of consent should be documented.

Subjects may be discontinued from the study at any time at the discretion of the Investigator.

Reasons for discontinuation include:

- Severe non-compliance to study protocol procedures, as judged by the Investigator and/or Sponsor.
- Subject is lost to follow-up. A subject will be considered lost to follow-up if he/she fails to come for consecutive scheduled visits and if he/she is not possible to contact by site staff despite several attempts.
- Significant adverse event (AE) posing a risk for the subject, as judged by the Investigator and/or Sponsor.
- Pregnancy.

9.8.2 *Procedures for discontinuation of a subject from the study*

If a subject withdraws consent, the Investigator must ask the subject if he/she is willing, as soon as possible, to be assessed according to the procedures scheduled for the end-of-study visit. A subject who prematurely discontinues participation in the study will always be asked about the reason(s) for discontinuation and the presence of any AEs. Any ongoing AEs will be followed as described in Section 11.6.10.

The primary reason for discontinuation/early withdrawal must be specified in the eCRF.

9.8.3 Subject replacement

Subjects who are prematurely withdrawn from the study may be replaced at the Sponsor's discretion after consultation with the Investigator..

9.9 Randomization

On Visit 2, the subjects will be randomized to a treatment sequence. As this is an open study, the treatment sequence to which each subject is allocated for will be recorded in the eCRF. A computer-generated randomization list will be created using SAS Proc Plan, SAS Version 9.4. The randomization list will contain subject number, treatment sequence, period, and treatment.

The randomization list will be generated by CTC or delegate and provided to the packing company. The original randomization list will be kept by the randomizer. A copy of the randomization list will be provided to the clinic. A coded copy of the randomization list will be generated, i.e. a list where the treatment is blinded, and this coded list will be provided to the bioanalytical laboratory and to the pharmacokineticist.

10 TREATMENTS

The IPs, both test- and reference products are supplied by Swedish Match AB.

10.1 Identity of investigational products

- 1: ZYN Moist Smooth containing 7 mg nicotine per portion
- 2: ZYN Moist Smooth containing 9 mg nicotine per portion
- 3: ZYN Moist Smooth containing 11 mg nicotine per portion
- 4: ZYN Dry Mini Smooth containing 3 mg nicotine per portion

CONFIDENTIAL

5: ZYN Dry Mini Smooth containing 6 mg nicotine per portion

10.2 Identity of reference product

6: Longhorn Pouch Natural containing 18 mg nicotine per portion

10.3 Manufacturing, packaging and labelling

The production sites and batch ID for the IP and reference product will be documented in trial master file.

The IP will be manufactured and packaged in compliance with the Swedish law on food production.

The IP will be transferred from the original container, weighed and individually packaged in identical sealed food approved test containers at the Swedish Match analytical lab.

The containers will be labelled with unique identification numbers by Swedish Match in accordance with the randomization list.

10.4 Conditions for storage

The IP will be stored in an access-controlled storage area at CTC, at refrigerated temperature (4-8°C).

The temperature is recorded continuously by an automatic temperature control system.

10.5 Preparation and accountability

The IP will be dispensed according to the randomization list by the site personnel. Before administration to the subjects, the IP should be placed in room temperature for at least 30 minutes to allow the IP to adapt to room temperature.

The Investigator will maintain a Storage and Accountability Log as well as a Dispensing Log detailing the dates and quantities of study IP received, prepared for and used by each subject and study medication returned or destroyed at the end of the study. Any discrepancies between prepared and returned IP must be explained and documented. Products deliberately and/or accidentally destroyed by the site or the subject must be accounted for.

10.6 Treatment administration

A single dose will be given in the morning of each treatment visit.

10.7 Treatment compliance

All IP will be administered at the research clinic under medical supervision to ensure compliance.

10.8 Return and destruction of investigational medicinal products

Any unused study IP and all empty containers will be destructed at the site upon confirmation from the Sponsor. The Monitor will perform final IP accountability reconciliation at the study end to verify that all unused IP is adequately destroyed and documented.

11 STUDY ASSESSMENTS

The study assessments are described in the sections below and the timing of these assessments are detailed in the schedule of events (Table 8.1-1 and Table 8.1-2, Section 8.1).

11.1 Recording of data

The Principal Investigator will provide the Sponsor with all data produced during the study from the scheduled study assessments. He/she ensures the accuracy, completeness, legibility, and timeliness of the data reported to Sponsor in the eCRF and in all required reports.

It is important that PK blood sampling occurs as close as possible to scheduled time. In order to achieve this, the timing priority order at a particular time point is:

- 1. IP pouch collection
- 2. Blood samples for PK
- 3. Blood samples for DBS PK
- 4. Urge to snus (VAS)
- 5. Pulse rate measure

Time points for PK blood sampling and VAS are outlined in Table 8.1-2.

See Section 11.3.1 for allowed deviation of actual time for PK sampling.

11.2 Demographics and other baseline characteristics

11.2.1 Informed consent

Signed informed consent must be obtained before any screening procedures are initiated. The informed consent procedure is further described in Section 14.3.

11.2.2 Demographic information

The following demographic data will be recorded: gender, age, ethnicity and race.

11.2.3 Medical/surgical history

Medical/surgical history will be obtained by subject interview in order to verify that the eligibility criteria are met.

11.2.4 History of nicotine use

History of snus use in terms of brand of snus, average consumption per day (last month), and duration of use (years) as well as history of smoking in terms of number of cigarettes per day (the last month) will be obtained by subject interview.

11.2.5 *Eligibility criteria*

Eligibility criteria should be checked during screening and verified before randomization. The criteria are specified in Sections 9.4 and 9.5.

11.2.6 Physical examination

A complete physical examination will include assessments of the head, eyes, ears, nose, throat, skin, thyroid, neurological, lungs, cardiovascular, abdomen (liver and spleen), lymph nodes and extremities.

11.2.7 Weight and height

Weight and height will be measured without shoes.

11.2.8 HIV and Hepatitis B/C

Subjects will be tested for HIV and hepatitis B/C prior to inclusion into the study. Any positive result will exclude the subject from participating in the study.

11.2.9 Pregnancy test

All females of child bearing potential will do a urine pregnancy test at screening as well as at all treatment visits.

11.2.10 Urine drug screen

Urine will be screened for drugs of abuse at time points outlined in the schedule of events (Table 8.1-1) using the AlereTM Drug Screen Test Panel. Additional random tests can be performed during the study period.

11.2.11 Alcohol breath test

An alcohol breath test will be performed at time points outlined in the schedule of events (Table 8.1-1). Additional random tests can be performed during the study period.

11.2.12 Baseline symptoms

A baseline symptom is defined as an event that occurs between the subject's signing of the ICF until the first administration of IP (i.e. an event that occurs during the screening period). Such events are not AEs and will be recorded as baseline symptoms in the Medical History Log in the eCRF.

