Besides risks related to the IPs, there may also be risks related to the medical devices used in the study e.g. indwelling venous catheters. However, these are devices that are used in routine medical care and the risk associated with their use is considered low and ethically justifiable. Study specific evaluations and sampling procedures, such as frequent blood-sampling, may cause transient discomfort but the risk is deemed to be low and ethically justifiable.

Risk assessment with regards to the COVID-19 pandemic:

Current recommendations from the authorities will be considered on a day-to-day basis. Ongoing risk evaluation, assessment sessions with Sponsors, Investigators, CRO/vendor representative members to align on local restrictions, impact assessment, contingency plans and study-specific risk mitigation strategies will be made to safeguard the study conduct and the safety of the study subjects. This study is a short-term study including a healthy population. Hence, study participation is not expected to confer increased risks to the study subjects in terms of COVID-19 exposure.

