11.6.1 Definition of adverse event

An AE is defined as any untoward medical occurrence in a subject administered a medicinal product (in this case an investigational product) and which does not necessarily have a causal relationship with this treatment. An AE can therefore be any unfavourable and unintended sign (including an abnormal laboratory finding), symptom, or disease temporally associated with the use of a medicinal product, whether or not considered related to the investigational product.

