11.6.3 Time period and frequency for collecting adverse events

All AEs (including SAEs) will be collected from the start of IP administration until the endof-study visit.

Any AE with start date on the day of IP administration must be recorded with start time.

At the end-of-study visit, information on new AEs or SAEs, if any, and stop dates for ongoing during events must be recorded as applicable.

Investigators are not obligated to actively seek AEs or SAEs after conclusion of the study participation. However, if the Investigator learns of any SAE, including a death, at any time after a participant has been discharged from the study, and he/she considers the event to be reasonably related to the study intervention or study participation, the Investigator must promptly notify the Sponsor.

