11.6.5 Assessment of causal relationship

The Investigator must assess the causal relationship between an AE and the IP using the definitions below and record it the AE Log of the eCRF:

Probable	The event has a strong temporal relationship to the IP or recurs on re- challenge, and another aetiology is unlikely or significantly less likely.
Possible	The event has a suggestive temporal relationship to the IP, and an alternative aetiology is equally or less likely.
Unlikely	The event has no temporal relationship to the IP or is due to underlying/concurrent illness or effect of another drug (that is, there is no causal relationship between the IP and the event).

An AE is considered causally related to the use of the IP when the causality assessment is probable or possible.

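### Harm from a study procedure between consent and the first dose is excluded from AE and SAE reporting, and relation to a study procedure is never rated

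*Protocol*

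**What the plan says.** **Named risks.** Protocol 6.3 states that "there may also be risks related to the medical devices used in the study e.g. indwelling venous catheters". It adds that study procedures "such as frequent blood-sampling, may cause transient discomfort but the risk is deemed to be low and ethically justifiable".

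**Before the first dose.** Section 11.2.12 covers everything from consent to the first product administration: "Such events are not AEs and will be recorded as baseline symptoms in the Medical History Log in the eCRF". Section 11.6.3 agrees: "All AEs (including SAEs) will be collected from the start of IP administration until the endof-study visit". The footnotes to Tables 8.1-1 and 8.1-2 follow the same boundary. Baseline symptoms run until dosing at Visit 2, and pre-dose AE recording applies at Visits 3 to 7 only.

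**After the first dose.** Section 11.6.1 takes in any untoward occurrence, "whether or not considered related to the investigational product".

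**Seriousness.** Section 11.6.2 defines an SAE as an AE that meets one of the listed criteria. Section 11.6.9 sets the 24-hour duty. The alert is triggered when an event in the AE Log is saved as serious.

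**Causality.** Section 11.6.5 asks only about the product, on a scale of *Probable*, *Possible* and *Unlikely*. *Unlikely* is described as: "The event has no temporal relationship to the IP or is due to underlying/concurrent illness or effect of another drug". A bracketed gloss then says that the category means the product did not cause the event. In 11.6.8, relation to the product is the only causality item recorded for each AE.

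**After the study.** For an SAE learned of after discharge, 11.6.3 applies a wider test: if "he/she considers the event to be reasonably related to the study intervention or study participation, the Investigator must promptly notify the Sponsor".

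**The concern.** The protocol identifies procedure risk and then sets the start of AE collection so that the first exposures to that risk fall outside it. A subject who has a serious complication of the screening draw, or of the catheter at Visit 2 before dosing, would be filed under medical history, where no rule in 11.6 calls for a report within 24 hours. The boundary depends on the first dose and not on the cause of the event, so an identical complication has a different status one visit later.

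The second weakness is attribution. When an event follows dosing closely but the investigator thinks the needle or catheter more likely caused it, the listed criteria have no place for that judgement, and no field records it. What is at stake is prompt reporting of serious procedural harm and clean attribution of AEs. The AUCinf comparison is not affected.

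**Working it through.** The protocol gives no figure on this point to reproduce. The check is a cross-reading of the sections plus a count of exposure.

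**Step 1: which procedures precede the first dose**
- Screening: blood tests for HIV and hepatitis B/C (9.5 criterion 5, 11.2.8).
- Visit 2: catheter and pre-dose plasma sample, taken up to 15 minutes before dosing (11.3.1, Table 8.1-2).
- Visit 2: a pre-dose finger prick, for any of the 18 DBS subjects whose first product is one of the three DBS products (11.5.2).

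Section 11.2.12 equates its window with the screening period. In fact the window extends into Visit 2, after screening (Day -28 to -1) has ended.

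**Step 2: status of a serious procedural event at each stage**

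| When | AE? | SAE route with 24-hour report? |
|---|---|---|
| Screening draw | No (11.2.12) | None defined (11.6.2, 11.6.9) |
| Visit 2, pre-dose | No (11.2.12) | None defined |
| Visit 2, post-dose | Yes (11.6.1) | Yes |
| Visits 3 to 7, pre-dose or post-dose | Yes (Table 8.1-2, 11.6.1) | Yes |
| After discharge | AEs not actively sought | Prompt notification if judged related to the intervention or to participation (11.6.3) |

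**Step 3: how much exposure lies outside the AE window**
- Plasma samples per visit: pre-dose, 5, 10, 15, 30 and 45 min, 1 h, 1 h 15, 1 h 30, 2 h, 4 h and 6 h = 12.
- Per subject: 12 × 6 visits = 72. Before the first dose: 1. Share outside: 1/72 = 1.4%. Inside: 71/72 = 98.6%.
- Catheter placements, assuming one per treatment visit (the protocol does not say): 36 subjects × 6 = 216, of which 36 precede the first dose; 36/216 = 1/6.
- Screening draw: about 42 people screened (9.3), so it also reaches people who are never randomised.

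**Step 4: the causality scale applied to one example**

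Take a near-faint during early sampling, with the pouch in place and venepuncture judged the more likely cause.
- *Probable* requires other causes to be improbable or clearly less probable. Not met.
- *Possible* requires the other cause to be no more likely than the product. Not met.
- *Unlikely*, by its listed criteria, requires no link in time, an illness or another drug. Not met.
- *Unlikely*, by its bracketed gloss, requires only that the product did not cause the event. Usable if the investigator concludes that.

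The listed criteria leave the case out, and the gloss lets it in. Relation to the procedure is recorded in neither case.

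**The case against.** The strongest defence is that this is a consistent convention. Sections 11.2.12 and 11.6.3 and both schedule tables start AE collection at the first dose, and 11.6.1 defines an AE in a subject who has been given the product. The post-discharge clause covers a different period and contradicts nothing. Section 6.3 rates the procedural risk as low. All of this stands, and it is why the point is a gap and not a contradiction.

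Section 4.1 also says that a medical emergency during the study usually constitutes an SAE and is to be reported as one. A site might act on that before dosing. But 4.1 covers emergencies only, says usually, and refers to 11.6.9 for the procedure, which runs through the AE Log. It does not override 11.2.12.

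Three stronger readings are tempting and are not supported:
- **The AE rules cannot capture procedure harm.** They do from the first dose onward, which covers 71 of 72 plasma draws per subject. Earlier events are still entered in the eCRF as baseline symptoms, so they are recorded and can reach the sponsor with the study data. What is missing is AE/SAE status and the 24-hour route.
- **Procedural events must be rated *Possible* and so counted as product-related.** Nothing forces this. *Possible* excludes a more likely alternative, and the gloss under *Unlikely* is available.
- **The by-treatment AE profile is contaminated.** Section 17.8 summarises incidence by SOC and PT by treatment and plans no split by causality, so a different rating would not change those counts. Venous sampling is the same at all six visits and the order of products is randomised. Only the finger prick is unequal (three products, 18 subjects), and the protocol gives no basis for saying that it adds nausea or dizziness to a material extent.

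**Conclusion.** The concern holds in a limited form. A serious event caused by a study procedure between consent and the first dose is by definition not an AE, hence not an SAE, and 11.6 gives it no 24-hour route. This is so even though 6.3 names the procedures as risks and the same pre-dose event at Visits 3 to 7 is an AE. In addition, relation to a study procedure is never rated, and the causes listed under *Unlikely* leave it out.

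The catheter share in the count rests on the one-placement-per-visit assumption. The count measures exposure; the protocol gives no event rates from which to project harm. The gap matters for subject protection and for the clarity of attribution. It is a cheap improvement to safety reporting and not a threat to the trial's conclusions.

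**What to change.** - **11.2.12 and 11.6.3:** from signing of the consent form, record any event judged related to a study procedure as an AE, or as an SAE reported under 11.6.9. Keep the baseline-symptom label for all other pre-dose events. Align 11.6.1 and the footnotes to Tables 8.1-1 and 8.1-2.
- **11.6.5 and 11.6.8:** extend *Unlikely* to cover a more likely alternative cause, such as a study procedure, and add a yes/no field for relation to a study procedure.
- **17.8:** list pre-dose procedure-related events separately. They belong to no treatment, and people who are screened but never dosed are outside the safety set in 17.3.1.

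The cost is a few sentences of protocol text, one eCRF field and a few more AE entries. No visit, sample or assessment is added.
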